### **7.3.2 Storage**

Store unreconstituted product at controlled room temperature 20° to 25(C(68° to 77( F). Store solution at controlled room temperature 20° to 25(C (68° to 77( F) and protect from light. Use solution only if it is clear. Unused solution should be discarded after 3 days.

### **7.3.3 Dispensing of Study Drug**

Drug will be prepared and dispensed by the Investigational Drug Services Pharmacy at the Nucleus Network (Prism Clinical Research) center.

## **8 Study Device- CRONO P**

CRONO P is an ambulatory infusion pump with reservoir, intended for bolus subcutaneous administration for long-term treatment with glucocorticoids.

A mechanism pushes against the reservoir's rubber plunger, enabling the pump to combine high delivery pressure with excellent precision while administering the drug.

An innovative infusion control system allows the pump to automatically restart and finish an infusion after an occlusion has been removed.

CRONO P has a liquid crystal display (LCD) which provides the doctor and patient with useful information regarding the settings, operations and diagnostics of the pump.

The CRONO P is designed to be used with any commercially available infusion sets with luer lock connector so that the decision of which set to use could be made by the healthcare professionals following the patient. For this protocol we are going to use the following set:

### **Comfort and Inset Subcutaneous Infusion Sets made by Unomedical (510K #: K051264)**

The Unomedical infusion set uses the standard luer lock which is compatible with all pumps that use a luer lock, like the Cane` Crono P that we are using in our study. The Unomedical set is commercially available and cleared for use in the United States. This infusion Set is an all-in-one straight-set infusion system. The 90-degree soft cannula is pre-loaded in an automatic spring inserter, to allow for one-handed insertions and it also has a built-in needle cover.

## 9 Risks and Benefits

### 9.1 Potential Risks

#### Risks of Hydrocortisone

While there are risks associated with chronic corticosteroid use, this CAH patient population does not produce adequate levels of cortisol and therefore require this treatment for survival. Patients with CAH, whether in the study or not, take corticosteroids every day of their life. The potential risks specific to this study are mainly dermatologic: Allergic dermatitis, cutaneous and subcutaneous atrophy, erythema, hyperpigmentation, hypopigmentation, rash, sterile abscess, striae, urticaria.

Potential risks of hydrocortisone in children and adults not specific to our study population and study design include:

- Gasping syndrome due to the presence of benzyl alcohol in the injectable cortisol.
- Allergic reactions: allergic or hypersensitivity reactions, anaphylactoid reaction, anaphylaxis, angioedema.
- Cardiovascular: Bradycardia, cardiac arrest, cardiac arrhythmias, cardiac enlargement, circulatory collapse, congestive heart failure, fat embolism, hypertension, hypertrophic cardiomyopathy in premature infants, myocardial rupture following recent myocardial infarction (see WARNINGS), pulmonary edema, syncope, tachycardia, thromboembolism, thrombophlebitis, vasculitis.
- Dermatologic: Acne, allergic dermatitis, burning or tingling (especially in the perineal area, after intravenous injection), cutaneous and subcutaneous atrophy, dry scaly skin, ecchymoses and petechiae, edema, erythema, hyperpigmentation, hypopigmentation, impaired wound healing, increased sweating, rash, sterile abscess, striae, suppressed reactions to skin tests, thin fragile skin, thinning scalp hair, urticaria.
- Endocrine: Decreased carbohydrate and glucose tolerance, development of cushingoid state, glycosuria, hirsutism, hypertrichosis, increased requirements for insulin or oral hypoglycemic agents in diabetes, manifestations of latent diabetes mellitus, menstrual irregularities, secondary adrenocortical and pituitary unresponsiveness (particularly in times of stress, as in trauma, surgery, or illness).
- Fluid and electrolyte disturbances: Congestive heart failure in susceptible patients, fluid retention, hypokalemic alkalosis, potassium loss, sodium retention.
- Gastrointestinal: Abdominal distention, bowel/bladder dysfunction (after intrathecal administration), elevation in serum liver enzyme levels (usually reversible upon discontinuation), hepatomegaly, increased appetite, nausea, pancreatitis, peptic ulcer with possible perforation and hemorrhage, perforation of the small and large intestine (particularly in patients with inflammatory bowel disease), ulcerative esophagitis.
- Metabolic: Negative nitrogen balance due to protein catabolism.
- Musculoskeletal: Aseptic necrosis of femoral and humeral heads, Charcot-like arthropathy, loss of muscle mass, muscle weakness, osteoporosis, pathologic fracture of long bones, postinjection flare (following intra-articular use), steroid myopathy, tendon rupture, vertebral compression fractures.
- Neurologic/Psychiatric: Convulsions, depression, emotional instability, euphoria, headache, increased intracranial pressure with papilledema (pseudotumor cerebri) usually following discontinuation of treatment, insomnia, mood swings, neuritis, neuropathy, paresthesia, personality changes, psychic disorders, vertigo. Arachnoiditis, meningitis,

paraparesis/paraplegia, and sensory disturbances have occurred after intrathecal administration (see WARNINGS, Neurologic).

- Ophthalmic: Exophthalmoses, glaucoma, increased intraocular pressure, posterior subcapsular cataracts, rare instances of blindness associated with periocular injections.
- Other: Abnormal fat deposits, decreased resistance to infection, hiccups, increased or decreased motility and number of spermatozoa, injection site infections following non-sterile administration (see WARNINGS), malaise, moon face, weight gain.

## **9.2 Potential Risks of the CRONO P Device**

The major risk of this device that could cause serious harm to the patient is the use of incorrect settings and/or incomplete understanding of the operational functions and of the alarms.

## **9.3 Methods to minimize risk**

Subjects will be monitored as per standard of care during treatment with oral cortisol. During the treatment with the SQHC pump, subjects will be monitored inpatient through physical exams for the first 36 hours. Following discharge, for the first four changes in SQ infusion site, a nurse coordinator will travel to the patient's home to evaluate proficiency in changing the injection site; to collect blood for cortisol, 17OHP, ACTH and D4A concentrations; and to inspect the injection site integrity. All patients will be seen at home twice during the first week and second week and once a week thereafter while on the pump. As an additional safety measure for monitoring pump failure that does not trigger an alarm, families will be given and instructed on how to use an automatic, upper arm blood pressure monitor with a cuff appropriate for the child's size. One week prior to the SQHC pump treatment, patients while on oral HC will measure and log child's blood pressure daily in the morning, after 5 minutes rest. When the child is on the pump, families will be instructed to measure and log the child's blood pressure daily. If the mean arterial pressure [MAP =  $[(2 \times \text{diastolic}) + \text{systolic}] / 3$ ] is less than 20 percent of the lowest MAP observed during oral treatment, the blood pressure will be measured 2 more times at 5-minute intervals. Instructions will be provided to the families to notify the PI if 2 of the 3 MAP measurements are below 20 percent of the lowest MAP obtained during oral HC treatment. Parents will be asked to inspect the injection site, tubing, and syringe volume. If no issues are identified and if the blood pressure remains outside the appropriate range after three measures, the parents will be instructed to bring the child to the clinic for clinical evaluation and assessment of pump function. Subjects and their parents will be instructed to contact the Principal Investigator immediately if they develop any signs of symptoms of adrenal insufficiency (e.g. fatigue, nausea, dizziness). The PI can be reached 24 hours a day by her pager number.

The parents of the subjects will be thoroughly trained on the use of the pump, the infusion sets which will be used, and the operational functions of the alarms.

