Another challenge with HC therapy is its short median elimination half-life in CAH children of 58 min (range: 41-105 min) allowing most of the HC dose to be eliminated from the body within 4-5 hrs. This is of particular concern as the cortisol concentration from the evening HC dose washes out overnight resulting in unopposed ACTH-stimulated adrenal androgen production and significant hyperandrogenemia each morning when ACTH is at its peak (~0600). Because of HC's short half life, the recommended 3 times a day dosing schedule is inadequate and children are inevitably exposed to alternating periods of hypo- and hypercortisolemia throughout each day (**Fig. 3**). Hypocortisolemia leading to hyperandrogenemia, besides causing genital virilization, can also lead to premature fusion of the growth plates, precocious puberty, adrenal rests, polycystic ovarian syndrome, infertility and endothelial dysfunction. Working memory performance and executive function are lower in children with CAH than in unaffected relatives and quality of life is reported to be reduced. Hypercortisolemia or overtreatment also have untoward long-term effects, such as osteoporosis, short stature, insulin resistance and increased risk for cardiovascular disease. Increasing the challenge of treatment is the interindividual variability of pharmacokinetic (PK) and pharmacodynamic (PD) response to HC due to variations in glucocorticoid receptor and tissue sensitivity. For example, about 7% of the general population harbor polymorphisms in the human glucocorticoid receptor that enhance responsiveness to GCs.

[figure not shown]
[figure not shown]

Fig 3. 24 hrs cortisol profiles of 5 patients on 3 times a day HC dosing (0800, 1400, 2000). Shaded area = 95% confidence intervals of normal control subjects (Maguire, et al, 2007)

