## **4 Study Design**

This is an open-label, non-randomized crossover feasibility trial which will compare oral HC administration with SQHC pump administration in pediatric patients with CAH. Up to twelve children (eight analyzable) with CAH, ages 3-18 years, will have serial cortisol, 17OHP, ACTH and D4A serum concentrations determined over 24 hours while taking conventional oral therapy (Admission 1).

Admission 2 will serve three purposes: a 33-hr SQHC pump evaluation period, patient and parent training with the pump, and a 24-hr PKPD study. During admission 2, we will use each patient's total daily dose (TDD) of HC to determine the doses to be delivered during the 33-hr period. The 24-hr schedule and percentage of the TDD of HC will be as follows: approximately 60% of the TDD of HC will be delivered in 3 equal pulses at 0300, 0600 and 0900. Another 35% will be delivered in 3 equal pulses at 1200, 1500 and 1800 and the remaining 5% at 2100 and 2400. Following delivery of the 9:00 pm, 12:00 am, and 3:00 am pulses, a 24-hr PKPD study will be initiated at the 6:00 am pulse using the same sampling schedule of cortisol, 17OHP, ACTH and D4A as the first admission. After the 24-hr serum sample at 0600 the next morning, the pump will be disconnected and the subject will be sent home on their usual oral HC dosing regimen.

After the SQHC pump therapy PKPD study during admission 2 at week 7, an analysis of the pattern of concentrations will be performed as a safety check. If the cortisol or adrenal steroid concentrations

are generally within acceptable ranges (defined in Aim 1), the same pump settings will be used when initiating the ambulatory pump phase at week 9. If concentrations are outside acceptable ranges, the initial SQHC pump settings will be adjusted from the Admission 2 dosing as needed to attain acceptable concentration ranges. Individual pulse doses may be increased or decreased but the frequency of pulses will be fixed to every 3 hours. After determining appropriate SQHC pump settings, the subjects will return to clinic at week 9 to initiate the 6-week SQHC ambulatory pump therapy phase.

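### Section 9.3 asks for a syringe-volume check only after low blood pressure, a trigger that a silent overnight pump stop is not shown to reach at the first morning check

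*Combined protocol and SAP*

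**What the plan says.** Section 9.3 presents the daily blood pressure log as an added layer against pump failure without an alarm. In the week before the pump phase, "patients while on oral HC will measure and log child's blood pressure daily in the morning, after 5 minutes rest". For the pump phase: "When the child is on the pump, families will be instructed to measure and log the child's blood pressure daily". No clock time is given there, and neither reading is tied to a dose or a pulse.

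The comparator is "the lowest MAP observed during oral treatment", with a 20 percent margin. A low reading leads to two repeats, and two low values out of three lead to a call to the PI. The direct look at the equipment comes at that point in the sequence: "Parents will be asked to inspect the injection site, tubing, and syringe volume". Section 9.3 does not ask for it on other days. Sections 6.2.2.1 and 7.1.2 cover inspecting the solution and changing the syringe every 72 hours, not a daily volume reading.

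Section 2 says that on oral treatment "the cortisol concentration from the evening HC dose washes out overnight". Section 4 sets the starting pump schedule: "approximately 60% of the TDD of HC will be delivered in 3 equal pulses at 0300, 0600 and 0900", a further 35% in three equal pulses at 1200, 1500 and 1800, and 5% at 2100 and 2400.

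**The concern.** The syringe shows directly whether drug has left the pump. MAP shows it only indirectly, through a response whose size and speed the documents do not give. Section 9.3 puts the indirect sign first and makes the direct one conditional on it.

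The indirect sign may also be blunted. Because the lowest oral value is used, a single reading taken before the morning dose can set the reference for the whole pump phase. That reading would be taken with almost no cortisol in the body, which is also the state after an overnight stop. Any fall in MAP from overnight cortisol loss would then be on both sides of the comparison.

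At stake is how long a silent stop goes unnoticed in a cortisol-dependent child, aged 3 or older. After a missed first check, the next scheduled blood pressure reading is about a day later.

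**Working it through.** **Inputs.** Half-life 58 min, range 41-105 (Section 2). Pump shares of TDD (Section 4): 20% at 0300, 0600 and 0900; 11.67% at 1200, 1500 and 1800; 2.5% at 2100 and 2400 (equal split assumed). Oral doses at 0600/1200/1800 (Section 6.2.1.1) or 0800/1400/2000 (Fig. 3 legend, Section 2), equal thirds assumed. Solution 10 mg/ml (Section 6.2.1.4). Minimum TDD 10 mg (Section 5.2.2). Instant absorption and a 0700 pump reading are assumed.

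**The plan's own statement.** Section 2 says most of a dose is gone in 4-5 h. Share eliminated = 1 - 2^(-t/half-life). At 4 h and 5 h this gives 94.3% and 97.2% (58 min), 98.3% and 99.4% (41 min), 79.5% and 86.2% (105 min). The statement is reproduced.

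**Cortisol in the body.** Residual = sum of dose share x 2^(-minutes since dose / half-life), as % of TDD:

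| State | 58 min | Range, 41-105 min |
|---|---|---|
| Oral, 0600 before the dose, last dose 1800 | 0.006 | 0.0002-0.32 |
| Oral, 0700 before the dose, last dose 2000 | 0.01 | 0.0005-0.47 |
| Pump stopped after 2400, at 0700 | 0.02 | 0.002-0.30 |
| Working pump, at 0700 | 10.9 | 7.6-17.9 |
| Oral, 1 h after a 0600 dose | 16.3 | 12.1-22.6 |

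A pre-dose oral reading resembles the stopped pump, with both under 0.5%. A post-dose oral reading resembles the working pump.

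**Would the rule fire at the first check?** Read the limit as 0.8 x reference. Let D be the fractional fall in MAP caused by overnight loss of cortisol.

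- Pre-dose reference: ratio = (1 - D)/(1 - D) = 1.0, so overnight loss alone never triggers the rule.
- Post-dose reference: ratio = 1 - D, so it triggers only if D exceeds 20%. An assumed D of 5-15% gives 0.95-0.85, which is no alert.

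**Longer stops.** Fall needed from the working-pump level with a pre-dose reference = 1 - 0.8(1 - D). For D = 5, 10 and 15% this is 24, 28 and 32%, against 20% with a post-dose reference. The D values are assumptions; the documents give no MAP response.

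**Dose missed.** Stop after 2400: by 0700, 20 + 20 = 40% of TDD (2 pulses, 7 h since the last dose); by the next 0700, 40 + 100 = 140% (10 pulses, 31 h). Stop after 2100: 42.5% at 10 h, then 142.5% at 34 h.

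**What the syringe would show.** Undelivered volume by 0700 after a stop following 2400 = 0.4 x TDD / 10 mg per ml: 0.4 ml at 10 mg and 0.8 ml at 20 mg. Expected use over 24 h is TDD / 10 mg per ml, or 1.0 ml and 2.0 ml.

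**The case against.** A reader might infer that the reference is always taken in a washed-out state, so that the MAP check cannot detect an overnight stop. The documents do not support that. Section 9.3 says morning, not before the dose. Section 6.2.1.1 standardises the first dose at 0600 and expects only small shifts from usual times, so a 0700 home reading could well follow the dose. In that case the oral state (16.3% of TDD) is above the working pump (10.9%). The pump reading has no stated time either, and a reading later in the day would reflect a longer loss. The family instructions are not in the documents and may settle both timings.

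A second tempting inference is that retiming the readings would solve the problem. It would not at the first check: with D at 5-15% the rule stays silent under either reference.

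Nor is harm at the first check shown. For a stop after 2100 or 2400, the child is then 7-10 h past the last dose, against 11-12 h before the dose on an ordinary oral morning. Using the lowest oral value is also a defensible way to limit false alarms.

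Other layers exist: pump alarms and training, symptom calls to a PI reachable at all hours, daily calls in week 9, home visits with serum cortisol, and syringe changes every 72 hours.

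All of this stands. It limits what can be said about the reference. It does not answer why the one check that is independent of blood pressure waits for a low reading.

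**Conclusion.** The point holds in a limited form. Section 9.3 makes the equipment check conditional on a MAP trigger that a silent overnight stop is not shown to reach at the first reading, whichever reference is used. With a 0700 reading and the starting schedule, a stop after 2400 can pass with 40% of TDD missed and meet its next scheduled blood pressure check at 140%. The other layers may catch it sooner, but daily calls are planned only for week 9, and home visits become weekly after the second pump week.

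The reference problem is conditional: it arises if at least one oral reading precedes the morning dose. The loss of sensitivity in mmHg cannot be computed from the documents. If MAP does not respond within hours, D is near zero and the check can catch only longer stops; the case for a direct volume check is then stronger. The residuals rest on instant absorption and equal oral doses, and the missed-dose figures on unadjusted pump settings. The literal wording of the 20 percent limit is a separate matter.

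**What to change.** **Main change.** In Section 9.3 and the family instructions, have parents check and log syringe volume, with site and tubing, at every daily reading whatever the MAP. Give each family the expected delivered volume for the child's current settings, and ask them to call if the syringe falls short.

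**Secondary change.** Take the oral reference readings 1-2 h after the morning dose and the pump readings 1-2 h after the 0600 pulse, both rested, with extra readings for symptoms at any time. This makes the two comparable and mainly helps with longer stops. Matching is not exact, because oral and pump dose sizes differ. The cut-off and the lowest-value rule can stay.

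**Cost.** A short addition to 9.3 and the instructions, with the same cuff and the same number of readings. Families take on a brief daily look at the syringe and a reading window. A post-dose reference may be higher, so a few more alerts are possible. The shortfall must be legible: 0.4 ml is 4% of a 10 ml fill (0.4/10), and the documents do not give the syringe graduations. Syringe volume will not reveal a leak at the site, so the MAP check should remain.

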#### **6.2.2 Weeks 9-14 (SQHC Pump)**

### **6.2.2.1 Weeks 9-13**

Week 9 (outpatient visit) The patient will meet [name] and the study nurse coordinator at Nucleus (Prism) for initiating the 6-wk SQHC pump phase. The patient will have a physical exam and the nurse coordinator will review the patient's recorded daily blood pressure, subject diary, adverse events and any medications taken. It is our standard policy to make sure that families have parenteral hydrocortisone to use during emergencies. We will instruct the patients to call [name] before administering any parenteral dose during this phase. After the first four supervised home visits by the nurse coordinator, the family, as instructed will replace the HC infusion syringe and solution, and the site of SQ infusion every 72 hours. As with insulin, we recognize that there may be variability in drug absorption associated with different sites of SQ injection pump infusion therapy. Each subject will be evaluated for appropriate site for SQ infusion (i.e. gluteal area, abdominal area).. Parents will be instructed to visually inspect the parenteral HC solution for particulate matter and discoloration prior to administration into the pump.

After the outpatient visit, during week 9, the subject/family will be called on the days that the RN coordinator is not completing home visits. This call is the review pump use, adverse events and other questions or concerns.

Weeks 9-13: The nurse coordinator will visit subjects at home seven times for safety monitoring, which includes a nursing assessment, and measurement of cortisol, 17OHP, ACTH and D4A concentrations during the SQHC pump period. During the home visits, along with the blood draws, saliva will be collected and measured through VerOFy® cortisol (VCORT) with the remaining salivary sample sent to Quest Diagnostics for free cortisol measurements through LC-MS/MS assay. VCORT is IDE exempt per the requirements outlined in 21CFR812.2(c) and in 21CFR809.10(c). The nurse coordinator will complete their assessment and review the patient's recorded daily blood pressure, subject diary, adverse events and any medications taken. At Visit 13, an Actigraph Link accelerometer will be provided for monitoring daily activity and sleep patterns for one week.

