b PKPD: samples to Quest for cortisol (free & total), ACTH plasma, 17-OHP, D4A, & ACTH at all timepoints																			
c Urine collection of 20 mL q12h, store frozen at -80C																			
d Phone call will occur daily during week 9 (except for outpatient & home visit days)																			
e Phone call will occur once a week for weeks 15 through 18																			
f any of the study activities noted below may be performed per investigator discretion																			

Version 10 SEPT 2019

\* Schedule of events will follow as described above with a time window of +/- 1 day for completion of study visits

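### The home blood-pressure trigger for silent pump failure in section 9.3 is set at 20 percent of the child's lowest oral-phase MAP, when a fall of more than 20 percent was probably meant; as written it cannot give early warning.

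*Combined protocol and SAP*

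**What the plan says.** Section 9.3 (Methods to minimize risk) introduces the home monitor "As an additional safety measure for monitoring pump failure that does not trigger an alarm". Families log a daily morning pressure for one week on oral hydrocortisone, which supplies the child's baseline, and then a daily pressure on the pump. MAP is defined as (2 × diastolic + systolic) / 3. Three steps follow:

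- **Re-measure:** take two further readings, five minutes apart, if MAP "is less than 20 percent of the lowest MAP observed during oral treatment".
- **Notify the PI:** if two of the three MAPs are "below 20 percent of the lowest MAP obtained during oral HC treatment".
- **Come to clinic:** after the site, tubing and syringe volume have been inspected without finding a cause, "if the blood pressure remains outside the appropriate range after three measures".

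No range is defined for the third step. Section 6.2.1.4 refers back to 9.3 for the instructions, and the revision history records only that the monitor was added. No other section gives a numeric blood-pressure threshold.

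On scheduled contact during the pump phase, 9.3 says: "All patients will be seen at home twice during the first week and second week and once a week thereafter while on the pump". Note d to the schedule of events says: "Phone call will occur daily during week 9", apart from visit days.

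**The concern.** A value below 20 percent of a baseline is a fall of more than 80 percent. A value more than 20 percent below a baseline is a different and much milder event. The first two steps both use the former construction, so this is not one isolated slip. The surrounding procedure fits only the latter: repeating a reading, checking the tubing and then driving to clinic is a sensible response to a modest drop, not to a MAP in the teens.

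The measure is aimed at failures on which the device is silent. Section 7.1.3 has the family go back to oral hydrocortisone when the pump fails, but that helps only once the failure is recognised. After the second pump week, scheduled nurse contact falls to one visit a week, so about 7 days can pass between contacts. During that time this rule is the only numeric trigger for pump failure in the documents. Children as young as 3 are eligible, and section 9.4 classes the study as greater than minimal risk without direct benefit, so a stated risk-reduction step should work as written.

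**Working it through.** **Inputs.** The MAP formula and the 20 percent figure come from section 9.3. The documents give no blood-pressure values, so every baseline below is an assumption.

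**Formulas.** Let B be the child's lowest oral-phase MAP.

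- Trigger as written: 0.20 × B
- Trigger for a fall of more than 20 percent: (1 − 0.20) × B = 0.80 × B
- Ratio: 0.80 / 0.20 = 4, whatever B is

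**Across a range of assumed baselines (mmHg):**

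| Lowest oral-phase MAP | As written (0.20 × B) | Fall of more than 20 percent (0.80 × B) |
|---|---|---|
| 50 | 10 | 40 |
| 60 | 12 | 48 |
| 70 | 14 | 56 |
| 80 | 16 | 64 |
| 97 | 19.4 | 77.6 |

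**Worked example, assumed lowest reading 95/55.**

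- B = (2 × 55 + 95) / 3 = 205 / 3 = 68.3 mmHg.
- As written: 0.20 × 68.3 = 13.7 mmHg. Scaling both pressures by 0.20 gives 19/11; check: (2 × 11 + 19) / 3 = 41 / 3 = 13.7.
- Fall of more than 20 percent: 0.80 × 68.3 = 54.7 mmHg. Scaling by 0.80 gives 76/44; check: (2 × 44 + 76) / 3 = 164 / 3 = 54.7.

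Under the written rule, a child whose MAP had halved from 68.3 to 34.2 mmHg would not meet the re-measure criterion. Under the other reading, that child would have met it well before.

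**Is the threshold corrected anywhere?** Section 6.2.1.4 only points back to 9.3. Sections 4, 7.1.2 and 10.4 name low blood pressure as a clinical sign but attach no number to it. The clinic-visit step refers to a range given nowhere else, so the only number it can draw on is the same 20 percent rule. That link is the natural reading, but the protocol does not state it.

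**Context on exposure.** Section 2 gives a median half-life of 58 minutes, "allowing most of the HC dose to be eliminated from the body within 4-5 hrs". The share of a dose left is 0.5^(240/58) = 5.7% at 4 hours and 0.5^(300/58) = 2.8% at 5 hours. This shows that cover is lost quickly if delivery stops. It does not show how fast MAP would fall, and the documents give no such time course.

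**The case against.** The best reply is that this is loose wording, not a failed safeguard. A MAP of 10 to 19 mmHg is so implausible as a home trigger that staff training the families could be expected to read it as a 20 percent drop. Families act on an instruction sheet that is not in the documents and may carry the right rule.

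The check is also explicitly an extra layer. Other protections do not depend on it:

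- Families contact the PI at once for symptoms of adrenal insufficiency, and the PI can be reached 24 hours a day.
- Families change the syringe and infusion site every 72 hours.
- A symptom diary is kept throughout.
- Home visits include blood draws and site inspection.
- At those visits the nurse is to "review the patient's recorded daily blood pressure, subject diary, adverse events and any medications taken".

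A once-daily reading could not in any case be relied on to catch a failure within 4 to 5 hours, so the half-life comparison adds little.

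Much of this stands. The documents do not show that families lacked a workable warning, and the elimination figures are background only. It does not rescue the text. Parents apply the rule at home, the instructions should derive from the protocol, and a reader who follows 9.3 exactly gets a trigger that is wrong by a factor of four. That the wording is obviously unintended is a reason to correct it.

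**Conclusion.** The concern holds and should be fixed. As written, both numeric triggers in section 9.3 require an 80 percent fall in MAP and would not fire before circulatory collapse. The fourfold gap from the probable intended threshold is exact and does not depend on any assumed baseline; the mmHg figures do. Two points remain open: that a fall of more than 20 percent was meant is an inference the documents do not confirm, and the content of the family instructions is unknown. The finding is therefore about the protocol text. It does not establish that the safeguard failed in use.

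**What to change.** - In both trigger sentences of 9.3, replace the threshold with *more than 20 percent below (i.e., less than 80 percent of) the lowest MAP observed during oral treatment*, after the clinical team confirms the percentage.
- In the clinic-visit step, replace the undefined range with a reference to that same threshold.
- Give each family the pre-computed mmHg value for their child, so that no percentage has to be worked out at home, and check that the family instructions carry the same rule.
- As a minor alignment, section 6.2.1.4 ends daily readings at week 13, while 9.3 requires them while the child is on the pump. Change the former to run until the pump is removed.

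The cost is a wording amendment to 9.3, one phrase in 6.2.1.4 and a check of the instruction sheet. No extra visits, equipment or data are needed.
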